## B. Patient Population

Twelve clinically stable adult CF patients  $\geq$  to 18 years of age will be recruited and enrolled from the adult outpatient CF clinic at NJH. Additional subjects (up to 20) may be enrolled if any patient leaves the study. We expect to enroll an approximately equal number of males and females. Most CF patients in the Colorado CF clinics are of white, non-Hispanic origin and I anticipate this ethnic mix to persist in this study. Because sildenafil has not been formally studied in CF patients with moderate to severe CF lung disease, and it is now uncommon for children to develop severe disease I will limit enrollment to adult patients for this pilot study.

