*Exacerbations:* During the course of the study, any enrolled subject requiring hospitalization and/or intravenous antibiotics for a cystic fibrosis-related pulmonary exacerbation will be withdrawn from the study.

*Early Withdrawal:* In case of early withdrawal, an Early Withdrawal Visit will be scheduled within 7 days following the last dose of study medication. Unless medically contraindicated, CFQR, safety labs, serum pregnancy for all women, spirometry, a six-minute walk test and cycle ergometry test will be performed. Physical exam will be performed by a study investigator including weight, temperature, blood pressure, respirations and pulse oximetry. Any abnormal findings will be documented. All remaining study drug will be collected.

*Concomitant medications:* All subjects should continue the same medications throughout the study period, as medically feasible, with no introduction of new chronic therapies during or <4 weeks prior to enrollment. If a change in concomitant medications is required, the reason(s) for the change(s) will be recorded on the subject's CRF.

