#### *Secondary outcome measures:*

- Change in gas exchange and heart rate kinetics (VO2, VO2 VCO2, VE)
- Change in average daily activity (steps per day as measured by Fitbit)
- Change in average heart rate after study drug therapy (as measured by Fitbit)
- Change in cardiac hemodynamics
- Change in measures of pulmonary function (FEV1)
- Change in quality of life as measured by the CFQ-R
- Change in sweat test
- Changes in antibiotic regimen during study period

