#### G. Mechanism of monitoring patient safety

*Medical Monitoring and Adverse Events:* The medical monitor will perform interim analyses of the safety data. The first interim analysis will occur after five patients have been enrolled in the study protocol. Data will be reviewed with the principal investigator on a monthly basis. Adverse events that may occur within this study population are most likely to be related to the underlying disease process as patients with cystic fibrosis are frequently hospitalized for intravenous antibiotic administration during periods of pulmonary exacerbation. Therefore, hospitalization for worsening pulmonary function will not be considered an adverse event or serious adverse event in this study protocol. However, those patients will be withdrawn from the study. Study related adverse events that will occur will most likely be related to the vasodilator effects of oral sildenafil citrate therapy. We expect the incidence of severe headache or uncomfortable symptoms of vasodilation (flushing, nasal congestion, etc.) to be self-limited.

*Serious adverse events and reporting:* Serious adverse events relating to this sildenafil therapy would include myocardial infarction, stroke, death, or anaphylactic reaction related to sildenafil citrate therapy. No patients with known cardiac disease or sildenafil allergy will be included in the study. Serious adverse events relating to exercise testing would include life-threatening arrhythmia or death during exercise testing. If any serious adverse event occurs, the principal investigator or one of the other investigators will report the incident (and any decision to suspend or halt the protocol) to the medical monitor and NJH IRB immediately (within 24 hours of becoming aware). Protocol stopping criteria will include any sildenafil citrate-related death.

*Confidentiality:* Confidentiality will be maintained through the duration of the study via strict adherence to all HIPAA compliance regulations.

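### Withdrawing every subject who is hospitalised or given IV antibiotics for an exacerbation ends follow-up for an outcome-related reason, and the analysis section does not say how these subjects are handled

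*Combined protocol and SAP*

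**What the plan says.** - **Withdrawal rule.** Section D (Study Timeline, Exacerbations) says "any enrolled subject requiring hospitalization and/or intravenous antibiotics for a cystic fibrosis-related pulmonary exacerbation will be withdrawn from the study". Section G repeats it for hospitalised patients: "However, those patients will be withdrawn from the study".
- **Expected frequency.** Section G says "patients with cystic fibrosis are frequently hospitalized for intravenous antibiotic administration during periods of pulmonary exacerbation". No rate is given.
- **Safety counting.** Section G adds that "hospitalization for worsening pulmonary function will not be considered an adverse event or serious adverse event in this study protocol".
- **Last measurement.** After early withdrawal, "an Early Withdrawal Visit will be scheduled within 7 days following the last dose of study medication". Its content is set out as follows: "Unless medically contraindicated, CFQR, safety labs, serum pregnancy for all women, spirometry, a six-minute walk test and cycle ergometry test will be performed". Neither this text nor the schedule table lists a cardiac MRI or sweat test at that visit.
- **Additional subjects.** Section B plans twelve subjects and says "Additional subjects (up to 20) may be enrolled if any patient leaves the study".
- **Outcomes.** Section F names change in six-minute walk distance and change in maximum work as primary. The secondary list includes "Changes in antibiotic regimen during study period", without further definition.
- **Analysis.** Section F plans paired t tests of pre- against post-treatment values and a mixed model over the time points. It defines no analysis set, does not say how withdrawn or additional subjects enter, and does not say whether early-withdrawal values count as post-treatment values.
- **Stopping drug.** Under Criteria for Study drug Discontinuation, subjects who stop drug are asked to complete all visits. The Visit 3 text in section D instead removes from the study a subject whose drug is discontinued.

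**The concern.** The rule ends study participation, not only treatment, at an event driven by lung disease. Lung disease also drives walk distance, maximum work, FEV1 and quality of life, so those who reach Day 84 are a selected group. If sildenafil changes the risk of exacerbation, the selection differs by arm. Such a difference is plausible on the protocol's own account: the background section proposes anti-inflammatory effects, and the toxicity section reports exacerbation of dyspnea in 11% on sildenafil against 5% on placebo.

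Safety reporting may not fill the gap, because section G keeps these admissions out of the adverse event counts. The pilot's stated purpose is to supply estimates for a multicentre randomised trial. A 12-week change estimated mainly in subjects who stayed well would be a poor basis for that design.

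**Working it through.** The plan gives no power, SD, dropout rate or exacerbation rate, so there is no figure of its own to reproduce.

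**What remains measured after an exacerbation withdrawal** (visit text and schedule table)

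| Outcome | Post-baseline measurements planned for a completer | Left for a withdrawn subject |
|---|---|---|
| Walk distance, spirometry, CFQ-R | Visit 4, Visit 5 | Visit 4 if reached, and the Early Withdrawal Visit unless contraindicated |
| Maximum work (cycle test) | Visit 5 | Early Withdrawal Visit only, unless contraindicated |
| Cardiac MRI, sweat test | Visit 5 | None |
| Antibiotic changes | Whole study period | Up to the first IV course or admission |

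The Early Withdrawal Visit can fall up to 7 × 24 = 168 h after the last dose. At the half-life of about 4 h in the Study Drug section, that is 168 / 4 = 42 half-lives. This is the outer limit, and the visit may be much sooner.

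**How many subjects.** Inputs: N = 12 (section B); 3:1 allocation (section A), giving 12 × 3/4 = 9 and 12 × 1/4 = 3; 84 days of treatment (section D). The event rate r per patient-year is an assumption, taken as 0.5 to 1.5.

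- Risk of withdrawal over 84 days: p = 1 − exp(−r × 84/365)
- Expected withdrawals: 12 × p
- Chance of losing at least one of three placebo subjects: 1 − (1 − p)³

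| r (assumed) | p | Expected of 12 | At least 1 of 3 placebo |
|---|---|---|---|
| 0.5 | 10.9% | 1.3 | 29.2% |
| 1.0 | 20.6% | 2.5 | 49.9% |
| 1.5 | 29.2% | 3.5 | 64.5% |

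One placebo withdrawal removes 1/3 of the placebo follow-up MRIs. Section F justifies the placebo arm partly by the natural variability of such measures.

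**Possible bias if withdrawn subjects are left out.** Within an arm, completer mean minus all-subject mean = p × D, where D is how much worse the withdrawn subjects' mean change is. Assume D = 0.5 to 1.0 SD.

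- At p = 10.9%: 0.109 × 0.5 = 0.05 SD to 0.109 × 1.0 = 0.11 SD
- At p = 29.2%: 0.292 × 0.5 = 0.15 SD to 0.292 × 1.0 = 0.29 SD

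Between arms this cancels if risk and deficit are equal. With 10% against 30% withdrawn it is (0.30 − 0.10) × 0.5 to 1.0 = 0.10 to 0.20 SD, and its direction depends on which arm loses more. It arises only if the analysis omits the withdrawn subjects, which the plan neither states nor rules out.

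**The case against.** **The withdrawn subjects are not lost from the data.** A reader might infer that the rule removes them from the outcomes altogether. It does not. The Early Withdrawal Visit plans both primary outcomes, spirometry and CFQ-R, Visit 4 adds an interim value for anyone who reaches it, and a mixed model can use partial data. This stands for walk distance, spirometry and CFQ-R. It helps less for maximum work, which has no interim value, and not at all for MRI or sweat chloride.

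**Antibiotic changes remain observable.** A reader might also infer that the trial cannot see its own antibiotic outcome. The documents do not support this. Oral and inhaled changes made without admission do not trigger withdrawal. The IV start is itself the trigger, reasons for medication changes go on the CRF, and concomitant medication is reviewed at the early termination visit. What is lost is everything after the first IV course or admission, so follow-up is unequal.

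**Attrition is measurable.** It can be counted over everyone enrolled, so the rule does not distort the attrition rate itself. Nor does section B say that an additional subject displaces the data of the one who left.

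**Adverse events.** The Adverse Events section has a broad definition that includes new CF signs and symptoms, and its exception for serious events covers only exacerbations unrelated to study drug. Some exacerbations might therefore be captured despite section G. The two sections differ and must be reconciled.

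**Choice of target.** A small physiological pilot may reasonably aim at on-drug response, and a late Day 84 test in a subject off drug does not measure that. This is fair, but the plan does not state that target. Recording on- or off-drug status lets both questions be answered.

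**The rate is assumed.** Section G's remark on frequency concerns CF patients in general, whereas this trial enrols clinically stable subjects. The true risk could lie below the range shown.

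**Conclusion.** The concern holds as informative truncation of follow-up by a stated rule, combined with an analysis section that is silent on the subjects affected. Followed as written, the rule leaves these subjects with no Day 84 data, no follow-up MRI or sweat test, and at best one maximum work value that may reflect acute illness. It does not make antibiotic changes unobservable.

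The size rests on the assumed 0.5 to 1.5 events per patient-year: 1.3 to 3.5 of 12 subjects, and about a 29% to 65% chance of losing at least one of three placebo subjects. The bias of 0.05 to 0.29 SD within an arm depends further on the assumed deficit of 0.5 to 1.0 SD and on withdrawn subjects being omitted. The trial should act on this, because its main product is estimates for a larger trial.

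**What to change.** 1. **Follow-up.** Amend the Exacerbations paragraph in section D so that an exacerbation does not end follow-up. Seek the Visit 5 assessments (walk test, cycle test, spirometry, CFQ-R, MRI, sweat test) at Day 84 or as soon afterwards as the subject is clinically stable. This matches the statement under Criteria for Study drug Discontinuation that such subjects are asked to complete all visits. The Visit 3 text, the Exacerbations paragraph, section G and those criteria must be reconciled. Whether study drug continues is a clinical rule for the sponsor and is not proposed here.
2. **Analysis set.** State in section F that all randomised subjects stay in the mixed model, including those after whose departure an additional subject is enrolled.
3. **Antibiotic outcome.** Define it, and report IV courses and exacerbation hospitalisations by arm for all randomised subjects. Count any withdrawal for these reasons as an event.
4. **Early-withdrawal exercise values.** Label them by actual time and by on- or off-drug status, and do not treat them as 12-week values. Add a sensitivity analysis that includes them. Simply discarding them would create the completer selection described above.

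**Cost.** An amendment, and Visit 5 for about one to four subjects at the assumed rates. Those visits were planned for the original subjects but become extra if additional subjects are also enrolled. The protocol gives only the subject payment, $250 for Visit 5, so at most 4 × $250 = $1,000; MRI and exercise test costs are not stated. The statistical downside is added variability from measurements taken after an exacerbation and possibly off drug.

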#### Allocation and blinding

Patients will be randomized to sildenafil or placebo in a 3:1 fashion on study entry. The randomization sequence will be generated by [name] and provided directly to Belmar pharmacy. Investigators, subjects, laboratory, and study personnel will be blinded to treatment group.

#### Study Drug

Sildenafil (Revatio®) is FDA-approved for treatment (of pulmonary hypertension at an oral dose of 20 mg three times per day. In a large trial (n=278) of use of sildenafil for pulmonary hypertension published in the New England Journal of Medicine, escalating doses of sildenafil were used for 12 weeks (20 mg three times a day, 40 mg three times a day, and 80 mg three times per day.) There was no dose-related effect on the primary outcome. Although the initial group of subjects was treated for 12 weeks, improvements in the primary outcome were seen at 4 weeks.

Sildenafil is rapidly absorbed following oral administration in the fasting state with peak plasma concentrations occurring within 30-120 minutes (median 60 minutes) of administration. It is metabolized by the hepatic microsomal isoenzymes, CYP3A4 and cytochrome p450 2C9 (CYP2C9) to its major metabolite N-desmethyl

sildenafil. The metabolite accounts for approximately 20% of the pharmacologic effects of sildenafil. Both sildenafil and N-desmethyl sildenafil have a half-life of approximately 4 hours.

Sildenafil was the first PDEi approved by the FDA for treatment of pulmonary/cardiovascular disease. Tadalafil has the advantage of once daily dosing, and has been recently approved by the FDA for the treatment of PH. However, the short half-life of sildenafil makes it more appealing for study in a new patient population as exposure would be limited if short-term adverse reactions are observed.

Blinded study drug bottles will be packaged, labeled and shipped from Belmar pharmacy based on sequence number. Sildenafil will be stored and dispensed through the research pharmacy at National Jewish Health. An accurate accounting of dispensing and return of the study drug will be maintained by research personnel. Subjects will be instructed to return all unused study drug at the End of Study or Early Withdrawal visits. The PI holds the IND for the use of sildenafil in CF (IND #102639) and FDA reports will continue to be submitted annually.

### E. Outcome measures

Clinical laboratory tests will be performed including complete blood count with differential, comprehensive chemistry profile [including sodium, potassium, bicarbonate, blood urea nitrogen, creatinine, alanine aminotransferase (ALT), aspartate aminotransferase (AST), alkaline phosphatase, and total bilirubin) PT/INR, and serum pregnancy test (for females of child-bearing potential) will be performed at the screening and end of study visits for safety. Add HS-CRP

*Assessment of lung function:* Spirometry will be performed at the screening and end of treatment visits by a CF research coordinator according to ATS standards.

*Assessment of health related quality of life:* The CFQ-R, which has been shown to correlate with survival in CF, is designed to measure CF-specific patient-reported health-related quality of life. The 48 questions encompass five domains including physical symptoms, role functioning (e.g. school/work), psychological and emotional functioning, energy/fatigue, and social functioning. The four domains specific to CF that are measured are: eating disturbances, body image, embarrassment caused by symptoms, and treatment burden. This questionnaire has been validated in CF patients. The questionnaire will be administered at the first, interim and end of treatment visits.

*ECHO:* Echocardiogram will be performed at the screening visit to insure that the subject does not meet the exclusion criterion of frank pulmonary hypertension.

*Six Minute Walk Test:* 6MWT will be performed according to ATS standards.

*Cardiac MRI:* Cardiac MRI is a non-invasive imaging method to evaluate pulmonary artery blood flow and right heart structure and function. Pulmonary artery blood and right heart structure and function will be measured before and after treatment with sildenafil or placebo.

*Fitbit monitoring:* In order to determine whether sildenafil improves exercise tolerance on a day-to-day basis, subjects will wear a Fitbit for the 12 weeks of the study for monitoring.

*Sweat test:* Pilocarpine iontophoresis will be performed and sweat collected according to CFF standards. Sweat volume will be recorded. Sweat will be collected using the Macroduct® collection system. Samples will be shipped to the TDN Core laboratory in Aurora, CO for chloride concentration measurement.

*Cycle Ergometry Exercise Testing:* Previous studies of cardiopulmonary exercise testing (CPET) have consistently demonstrated decreased maximal work effort, peak oxygen consumption, and ventilatory reserve in patients with CF lung disease when compared to healthy, age-matched controls. Trained personnel will perform the test. Subjects will perform a standard ramped protocol on dynamically braked cycle ergometer. A SensorMedics metabolic cart will be used to measure breath-by-breath respiratory gas exchange with nose clip in place. Pulse-oximetry, ECG and heart rate will also be measured throughout the test.

The American College of Sports Medicine and the American Thoracic Society/American College of Chest Physicians guidelines for contraindications to cardiopulmonary exercise testing and exercise test termination criteria will be used. Patients with an FEV1 <40% predicted will be directly supervised by a physician during the exercise test. A physician will be immediately available for all other tests.

### Subject Reimbursement

In accordance with TDN recommendations, subjects will receive payment according to the schedule below:

Visit	Visit 1	Visit 2	Visit 3	Call 1	Visit 4	Visit 5	Call 2	Total
Payment	\$125	\$250	\$100	\$25	\$100	\$250	\$25	\$875

Subjects who complete the screening visit, will receive the \$100 payment regardless of whether they qualify for the study to compensate for their time and effort.

Subjects who live greater than 50 miles from the study site, will be reimbursed at the current standard mileage rate for medical purposes.

### F. Data Analysis

#### *Primary outcome measures:*

- Change in distance walked during six-minute walk test after sildenafil therapy
- Change in maximum work

#### *Secondary outcome measures:*

- Change in gas exchange and heart rate kinetics (VO2, VO2 VCO2, VE)
- Change in average daily activity (steps per day as measured by Fitbit)
- Change in average heart rate after study drug therapy (as measured by Fitbit)
- Change in cardiac hemodynamics
- Change in measures of pulmonary function (FEV1)
- Change in quality of life as measured by the CFQ-R
- Change in sweat test
- Changes in antibiotic regimen during study period

### **Data Collection Tools**

The site investigator will prepare and maintain adequate and accurate source documents designed to record all observations and other pertinent data for each subject treated with study drug.

Designated study personnel at each site will enter data from source documents corresponding to a subject's visit into the protocol-specific Research Electronic Data Capture (REDCap) electronic case report form (eCRF) as soon as the information corresponding to the visit is available. Each subject will be identified by site number, subject number and subject initials; subjects will not be identified by name in the study database or any study documents to be sent or transmitted out of National Jewish. All data entered during the course of the study must be reviewed and verified for completeness and accuracy by the site investigator.

The CFQR and CFRSD-CRISS will be completed by the subject at the visits outlined above. Data from the CFQ-R will be entered into the corresponding form for the subject's visit.

#### G. Mechanism of monitoring patient safety

*Medical Monitoring and Adverse Events:* The medical monitor will perform interim analyses of the safety data. The first interim analysis will occur after five patients have been enrolled in the study protocol. Data will be reviewed with the principal investigator on a monthly basis. Adverse events that may occur within this study population are most likely to be related to the underlying disease process as patients with cystic fibrosis are frequently hospitalized for intravenous antibiotic administration during periods of pulmonary exacerbation. Therefore, hospitalization for worsening pulmonary function will not be considered an adverse event or serious adverse event in this study protocol. However, those patients will be withdrawn from the study. Study related adverse events that will occur will most likely be related to the vasodilator effects of oral sildenafil citrate therapy. We expect the incidence of severe headache or uncomfortable symptoms of vasodilation (flushing, nasal congestion, etc.) to be self-limited.

*Serious adverse events and reporting:* Serious adverse events relating to this sildenafil therapy would include myocardial infarction, stroke, death, or anaphylactic reaction related to sildenafil citrate therapy. No patients with known cardiac disease or sildenafil allergy will be included in the study. Serious adverse events relating to exercise testing would include life-threatening arrhythmia or death during exercise testing. If any serious adverse event occurs, the principal investigator or one of the other investigators will report the incident (and any decision to suspend or halt the protocol) to the medical monitor and NJH IRB immediately (within 24 hours of becoming aware). Protocol stopping criteria will include any sildenafil citrate-related death.

*Confidentiality:* Confidentiality will be maintained through the duration of the study via strict adherence to all HIPAA compliance regulations.

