#### **Mechanism for Monitoring Patient Safety**

##### Study Oversight

The CFFT Data Safety Monitoring Board (DSMB) at the University of Arizona will provide trial oversight. A Data Monitoring Committee (DMC) a subcommittee of the DSMB will be formed for this trial in order to review the protocol, patient informed consent, and safety monitoring plan. During the study, the DMC will be responsible for real-time serious adverse event monitoring and reviewing interim safety reports to ensure the continued safety, scientific validity and merit of the trial and to make recommendations concerning continuation, termination or modification of the trial. The DMC will include at least two CF clinicians, and a biostatistician.

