##### Adverse Events (AE)

An adverse event will be defined as any unfavorable and unintended sign, symptom, or disease temporally associated with the use of Revatio® or other protocol-imposed intervention, regardless of attribution.

This definition will include the following:

- AEs not previously observed in the subject that emerge during the study period, including signs or symptoms associated with CF that were not present prior to the study period
- Complications that occur as a result of protocol-mandate interventions (e.g. sputum induction)

- Preexisting medical conditions (other than the condition being studied) judged by the investigator to have worsened in severity or frequency or changed in character during the protocol-specified AE reporting period

Subjects will be questioned and/or examined by the Investigator or her designee for evidence of adverse events.

Subjects having adverse events will be monitored with relevant clinical assessments and laboratory tests as determined by the investigator. All adverse events will be followed to satisfactory resolution or stabilization of the event(s.) Any actions taken and follow-up results will be recorded on the appropriate page of the CRF, as well as in the subject's source documentation. Follow-up laboratory results will be filed with the subject's source documentation.

For all adverse events that require the subject to be discontinued from the study, relevant clinical assessments and laboratory tests will be repeated until satisfactory resolution or stabilization of the event(s.)

A serious event will be determined as follows:

- It results in death
- It is life threatening
- It requires or prolongs inpatient hospitalization (with the exception of pulmonary exacerbation unrelated to study drug, see section G)
- It results in persistent or significant disability/incapacity
- It results in a congenital anomaly/birth defect in a neonate/infant born to a mother exposed to the investigational product
- It is considered a significant medical event by the investigator based on medical judgment

Grading of AEs will be as follows:

•Mild: Transient or mild discomfort (<48 hours); no interference with the subject's daily activities; no medical intervention/therapy required

•Moderate: Mild to moderate interference with the subject's daily activities; no or minimal medical intervention/therapy required

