•Severe: Considerable interference with the subject's daily activities; medical intervention/therapy required; hospitalization possible

To determine the causality of AE and SAE the follow guidelines will be assessed:

- **Definitely**: There is a plausible temporal relationship between the onset of the AE and administration of sildenafil, and the AE cannot be readily explained by the subject's clinical state, intercurrent illness, or concomitant therapies; and/or the AE abates or resolves upon discontinuation of sildenafil.
- **Probably**: There is a plausible temporal relationship between the onset of the AE and administration of sildenafil, and the AE follows a typical response to sildenafil, but a potential alternative cause may be present.
- **Unlikely**: There is a reasonable possibility that the onset of the AE is related to the administration of sildenafil, but an alternative cause seems more likely.
- **Unrelated**: Evidence exists that the AE has an etiology other than administration of sildenafil (e.g., preexisting medical condition, underlying disease, intercurrent illness, or concomitant medication); and/or the AE has no plausible temporal relationship to administration of sildenafil (e.g., cancer diagnosed 2 days after first dose of study drug.)

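### Section G removes pulmonary hospitalisation from AEs and SAEs unconditionally, while the SAE definition exempts only exacerbations unrelated to study drug and cites Section G for it

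*Combined protocol and SAP*

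**What the plan says.** Section G, Mechanism of monitoring patient safety, reasons that adverse events in this population will mostly reflect the underlying disease, since CF patients are often admitted for intravenous antibiotics during exacerbations. It then concludes that "hospitalization for worsening pulmonary function will not be considered an adverse event or serious adverse event in this study protocol", and adds that those patients will be withdrawn.

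Adverse Events (AE), later in the same document, defines an AE broadly and regardless of attribution. Its list of seriousness criteria includes: "It requires or prolongs inpatient hospitalization (with the exception of pulmonary exacerbation unrelated to study drug, see section G". The causality guidelines that follow are introduced with "To determine the causality of AE and SAE the follow guidelines will be assessed" and have four categories: definitely, probably, unlikely and unrelated.

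Several actions depend on SAE status:
- Section G has any SAE reported "to the medical monitor and NJH IRB immediately (within 24 hours of becoming aware".
- Medical Monitor has the medical monitor review all SAEs and the SAE report sent to the DMC chair within one business day of that review.
- Study Oversight makes the DMC responsible for "real-time serious adverse event monitoring and reviewing interim safety reports".
- DMC has SAEs reviewed as they occur.

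**The concern.** The two provisions cover overlapping events but differ in three ways: whether relatedness matters, which event is meant, and whether the exemption reaches AEs or only one SAE criterion. The document states no order of precedence. The SAE definition points to Section G as the source of its exemption, so a reader who follows the reference arrives at a sentence without the limit.

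At stake is the routing of an admission that the investigator thinks the drug caused. The possibility is not far-fetched on the protocol's own terms. Known Potential Toxicity of Study Drug lists worsening dyspnea at 11% on drug against 5% on placebo in earlier work, and Criteria for Study drug Discontinuation includes severe dyspnea at rest. Aim 2 asks whether treatment is safe, and Statistical analysis gives observing adverse events by arm as one reason for the 3:1 allocation.

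**Working it through.** The plan states no figure on this point, so the check applies each rule to the same events.

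| Hospitalised for | Judged | Section G sentence | SAE hospitalisation criterion |
|---|---|---|---|
| Pulmonary exacerbation | Unrelated | Not AE, not SAE | Exempt, not SAE |
| Pulmonary exacerbation | Related | Not AE, not SAE | Not exempt, SAE |
| Other worsening of lung function | Unrelated | Not AE, not SAE | Exemption does not name it |
| Other worsening of lung function | Related | Not AE, not SAE | Not exempt, SAE |

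**SAE status.** The rules agree only in the first row. In rows two and four they give opposite answers. Row three shows the mismatch in event term. If exacerbations never counted as adverse events, the exception in the SAE definition would be unnecessary. Its presence implies that a related exacerbation needing admission is meant to count.

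**AE status.** The conflict is weaker here. The AE definition's third bullet, on pre-existing conditions, leaves out worsening of the condition being studied. Against that, the lead definition applies regardless of attribution, and CF signs or symptoms not present before the study are included. The symptoms behind an admission can thus be AEs with their own causality rating, even if the admission is not.

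**What follows if Section G governs.** The 24-hour report, the report to the DMC chair and DMC review as events occur all start from an SAE. A related pulmonary admission sets off none of them unless it meets another criterion, such as death, threat to life, or a significant event in the investigator's judgement. The causality guidelines are written for AEs and SAEs, so nothing calls for a rating of the admission itself.

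**Illustration of size.** At 3:1, 12 subjects give 12 × 3/4 = 9 on sildenafil and 3 on placebo. If total enrolment reached 20 with an exact split (an assumption), the arms would be 15 and 5. Exact (Clopper-Pearson) 95% limits are as follows. For 0/n, the upper limit is 1 − 0.025^(1/n). For 1/n, the lower limit is 1 − 0.975^(1/n), and the upper limit p solves (1−p)^n + np(1−p)^(n−1) = 0.025.

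- n = 9: 1/9 = 11.1% (0.3 to 48.2%) becomes 0/9 (0 to 33.6%).
- n = 15: 1/15 = 6.7% (0.2 to 31.9%) becomes 0/15 (0 to 21.8%).

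The same arithmetic would apply to any single unrecorded event. It shows how much one event weighs in arms this small, not how likely the event is.

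**The case against.** The best defence is that the passages can be read together. The Section G sentence is drawn as an inference from disease-related admissions, so its authors may have meant only those. The SAE definition then states the limit openly and can be taken as the protocol's own gloss. The material after Section G sits under a nearly identical title with no new letter, so the qualifier may even lie inside Section G. This is a fair account of intent. It does not remove the conflict: the preceding sentence says what is most likely and is not a case-by-case test, the rule itself is unconditional, and a single section holding both statements would contradict itself.

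The other objections stand, and they limit the point:

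- A reader might infer that the two rules cannot be operated together. They can, if relatedness is judged first and the exemption applied second. The text does not set that order.
- A reader might infer that the meaning of unrelated is open, because the *Unlikely* category begins "There is a reasonable possibility that the onset of the AE is related to the administration of sildenafil". That definition goes on to say that another cause seems more likely. *Unrelated* is a separate named category, and the plain reading of the SAE exception is that category.
- A reader might infer that such admissions disappear from the record. They do not. The subject is withdrawn and has an Early Withdrawal Visit with safety laboratory tests, spirometry and examination. Reasons for medication changes go on the CRF, and changes in antibiotic regimen are a secondary outcome. Phone contact 2 provides follow-up of abnormalities felt to be study-related. Section G also says "Data will be reviewed with the principal investigator on a monthly basis", and interim safety analyses are planned.

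None of these safeguards requires a causality rating of the admission or starts SAE reporting because the subject was hospitalised.

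**Conclusion.** The contradiction is real and should be fixed. It is clear for SAE status: a drug-related pulmonary hospitalisation is an SAE under the definition and is not one under Section G. What is exposed is the SAE-triggered reporting and review. For AE status the conflict is weaker, and the event remains visible by other means.

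The size cannot be put as a probability, because the documents give no rate of drug-related pulmonary admission. The dyspnea figures (11% against 5%) come from earlier sildenafil experience; they support plausibility and are not a hospitalisation rate. Any effect is on descriptive safety counts and on who is told when, not on a formal test. The conclusion assumes that Section G is followed as written and that no other seriousness criterion is met. The DMC Charter is not part of these documents and might add reporting rules of its own.

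**What to change.** 1. Reconcile the Section G sentence with the SAE definition: the same event term in both places, the same condition that the event is unrelated to study drug, and an exemption that reaches only the SAE hospitalisation criterion.
2. State that relatedness of each pulmonary hospitalisation is judged with the protocol's existing causality categories before the exemption is applied.
3. Correct the cross-reference so that it leads to text carrying the condition.

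The cost is a short wording amendment and one causality entry per pulmonary admission in a study of 12 to 20 subjects. It concerns classification and reporting only and leaves the dosing and withdrawal provisions untouched.

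An optional addition is to list all pulmonary hospitalisations by arm in the safety reports. Relatedness is judged blind ("Investigators, subjects, laboratory, and study personnel will be blinded to treatment group"), so a listing by arm would let the DMC check how the exemption was used. This goes beyond removing the contradiction. Its downside is a few more recorded events that are probably due to CF.
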